7 GENERAL STATISTICAL CONSIDERATIONS

7.1 ANALYSIS SETS

The following analysis sets are planned for the study and will apply to the endpoints through the end of Phase 2. There are no prespecified analysis sets for Phase 3; all available data will be used to summarize Phase 3 endpoints.

7.1.1 ITT (Intention to Treat) Analysis Set

The ITT analysis set includes all subjects that are enrolled in the study. All safety analyses (other than primary analysis for primary safety endpoints) will be based on the ITT analysis set.

Statistical Analysis Plan

7.1.2 mITT (modified Intention to Treat) Analysis Set

The mITT analysis set is a subset of the ITT analysis set. The mITT analysis set will consist of subjects who have entered the hybrid closed-loop phase of the study successfully. The mITT analysis set will be used as the primary analysis set for all primary and secondary endpoints (both safety and effectiveness), and other clinical outcome data.

7.1.3 PP (Per Protocol) Analysis Set

The Per-Protocol (PP) analysis set is a subset of the mITT analysis set. Subjects will be included in the PP analysis set if they have a minimum of 80% system use during Phase 2 inclusive of manual and hybrid closed-loop (automated) modes over a minimum duration of 10 weeks and have completed the study without major protocol deviations. The PP analysis set will be used as supportive analysis for the endpoints. The following will be considered major protocol deviations:

- Major inclusion/exclusion criteria deviation
- Significant protocol non-compliance that may confound the study objective data (e.g., use of prohibited medications)

The list of subjects excluded from the PP analysis set will be determined prior to analysis of Phase 2 endpoints. If the PP analysis set does not differ from the mITT analysis set, separate analyses will not be presented.

7.2 CONTROL OF SYSTEMATIC BIAS

Several measures are incorporated into the study design to help minimize study bias as follows:

- This is a multi-center trial to help ensure that investigator or site or subject enrollment bias is minimized. Selection of subjects will be made from the Investigator's usual subject load. Consecutively eligible subjects should be enrolled into the study.
- 2) This document specifies appropriate statistical methodology to ensure that bias is minimized.
- 3) The effectiveness measures will be based on the direct output from the device or are analyzed at a NGSP certified central laboratory, ensuring objective reporting.
- 4) An independent Medical Monitor will adjudicate all SAEs and device-related adverse events; the Medical Monitor's assessment of adverse events will be used for regulatory reports, product labeling, and publications or presentation.

7.3 POOLING DATA ACROSS CENTERS

Up to 12 clinical sites will enroll subjects into the study. No single site should enroll more than 24 subjects. For the purposes of statistical analyses of primary effectiveness endpoints, data from all study centers will be pooled. The primary effectiveness endpoints

Statistical Analysis Plan

will also be presented by center. The appropriateness of pooling subjects across sites will be assessed graphically or utilizing an appropriate statistical test.

7.4 CALCULATION OF PERCENTAGE OF TIME IN RANGE

Several effectiveness endpoints involve calculation of percentage of time in a specific glycemic range. These endpoints will be based on the direct output from a device (either a CGM or The Omnipod Horizon[™] Automated Glucose Control System). The percentage of time in range (TIR) will be calculated as:

 $100 \times \frac{\# of CGM readings in range}{\# of evaluable CGM readings} = TIR\%$

The following CGM readings will be excluded from analysis, and therefore, from calculation of TIR endpoints:

- No glucose value is provided in the device output, such as due to an error or device deficiency during which the device does not record glucose readings
- CGM readings reported prior to start of standard therapy phase or after subject's discontinuation from HCL

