Subjects who meet all eligibility criteria and have completed all screening assessments will continue to enrollment. A subject is enrolled in the study upon placement of the first study CGM. Subjects that do not meet the eligibility criteria will not continue in the study and will be considered screen failures.

If for any reason a subject is no longer eligible for the study after the standard therapy phase has commenced but prior to the commencement of the hybrid closed-loop phase, the subject will not continue in study. No additional study assessments will be required. The reason for study exit will be clearly documented.

8 STANDARD THERAPY - PHASE 1

The standard therapy phase will commence after all standard therapy assessments are completed per **Visit 2** – see Table 1: Schedule of Assessments for Phase 1 and Phase 2.

During the standard therapy phase, subjects and/or parents/guardians will be asked to perform the following:

- Manage their diabetes at home per their usual routine
- Administer meal boluses per their usual dosing routine
- Change their sensor if a sensor fails, or as needed
- Calibrate their CGM, if required, per the manufacturer's instructions
- Monitor their capillary blood glucose (BG) per usual routine
- Give meal boluses. The timing of the bolus delivery will be per each subject's typical dosing routine.

Extending standard therapy past 14-days will not constitute a protocol deviation unless standard therapy extends past 30-days. If subjects extend beyond the 14-days, the most recent 14-days of data will be used in the endpoint analysis if the data meets the criteria defined for CGM use and data availability.

The standard therapy phase will be customized depending on the following subject profile:

- Current Dexcom G6 users
- Non-G6 users
- Pump Naïve users

Current Dexcom G6 Users

Current Dexcom G6 users will be required to participate in the assessments required as part of standard therapy (ST1/Visit 2) but may be exempt from wearing the study CGM for 14-days if the following criteria are met:

- Willing to provide 14-days of CGM data from the past 30-days
- Meet the success criteria of 80% CGM use during any consecutive 14-days in the past 30-days
- Must have $\geq 2,016$ CGM values during the 14-days

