If exemption criteria are not met, subjects and/or parents/guardians may choose to continue to collect data until they meet the criteria or will be required to participate in the entire 14-day standard therapy phase consistent with the requirements for non-G6 users.

Subjects deemed exempt from wearing the study CGM for 14-days will be immediately eligible to commence the hybrid closed-loop phase starting at Visit 4.

Non-G6 Users

All non-G6 users will be required to participate in the entire 14-day standard therapy phase. At the commencement of the standard therapy phase, subjects will be dispensed a CGM receiver that will be blinded and all user settable CGM alerts will be turned off. The device will record continuous glucose information over the 14-day period.

Pump Naïve Users

Subjects who are naïve to pump therapy will have the opportunity to participate in a saline trial during the standard therapy phase. A saline trial consists of wearing a cleared Omnipod® DASH System with the Pod filled with saline to simulate pump therapy. This would enable subjects and/or parents/guardians to familiarize themselves with the basic concepts of basal and bolus insulin delivery as well as provide the experience of wearing an on-body device prior to their participation in the hybrid closed-loop phase, if they choose to do so. This is optional and not required. If a pump naïve subject is also a current G6 user that meets the criteria as stated above, the subject will complete the saline trial prior to enrollment in the study.

8.1 Visit 2

Visit 2 represents the commencement of the standard therapy phase. All scheduled assessments will be performed according to Table 1: Schedule of Assessments for Phase 1 and Phase 2. This visit will include:

- Review of concomitant medications
- Average total daily insulin (approximately over the past 7 days)
- Average total daily basal insulin (approximately over the past 7 days)
- Average total daily bolus insulin (approximately over the past 7 days)
- Review of pump settings/MDI dosing
- Assessment of AEs
- Completion of questionnaires (see Table 2: Questionnaires):
 - WHO-5
 - Used to measure current mental well-being
 - DTSQs Parent
 - Used to measure satisfaction with diabetes treatment regimens
 - P-PAID-Child
 - Measures diabetes-related burden
 - Hypoglycemia Confidence Scale
 - Used to measure hypoglycemia unawareness, hypoglycemia frequency, severity and impact
 - PSQI

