1 PURPOSE

The purpose of this Statistical Analysis Plan (SAP) is to describe the statistical methodology that will be used to confirm the safety and effectiveness of the Omnipod Horizon[™] Automated Glucose Control System in children with type 1 diabetes aged 2.0-5.9 years. Should there be any discrepancy between the preschool study protocol and this SAP, the content of the SAP shall prevail.

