4.2 PRIMARY ANALYSIS

There are two primary effectiveness endpoints. The primary effectiveness endpoints will not be used to support labeling claims.

A1C

The end of Phase 2 (~13 weeks) A1C will be compared to baseline A1C as measured by the core laboratory by calculating the change from baseline in A1C at Visit 13 (~13 weeks) for each subject.

The change in A1C is calculated as the A1C at Visit 13 minus baseline A1C. The null hypothesis associated with this endpoint states that the mean change in A1C is greater than or equal to zero. Rejection of the null hypothesis indicates that the observed data support the alternative hypothesis that the mean change in A1C is less than zero (indicating improved glycemic control). The hypotheses associated with the first primary effectiveness endpoint are defined as:

H0: µ ≥ 0 H1: µ < 0

where μ is the mean of the per subject differences in A1C from baseline to Visit 13.

Percentage of Time in Range 70-180 mg/dL

The percentage of time in range (TIR) 70-180 mg/dL during Phase 2 of hybrid closed-loop will be compared to Phase 1 by calculating the change between the time in range percentages between Phase 2 and Phase 1 for each subject. The change is calculated as the percentage of time in range during Phase 2 minus the percentages of time in range

Statistical Analysis Plan

during Phase 1. The null hypothesis associated with this endpoint states that the mean change in percentage of time in range 70-180 mg/dL is less than or equal to zero. Rejection of the null hypothesis indicates that the observed data support the alternative hypothesis that the mean change in percentage of time in range 70-180 mg/dL is greater than zero. The hypotheses associated with the second primary effectiveness endpoint are defined as:

H0: µ ≤ 0 H1: µ > 0

where μ is the mean of the per subject differences in percentage of time in range 70-180 mg/dL during Phase 2 (hybrid closed-loop) compared to Phase 1 (standard therapy).

Both primary effectiveness endpoints will be tested independently of each other for statistical significance using a paired t-test at a one-sided significance level of 1.25%.

The modified Intention to Treat (mITT) analysis set will be the primary analysis set used to analyze the primary effectiveness endpoints. The results based on the Per Protocol (PP) analysis set will be considered supportive.

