6.1 ANALYSIS OF PERCENTAGE OF TIME IN RANGE

The analysis of secondary endpoints that summarize the percentage of time in range (TIR) will follow the analysis set forth for the primary effectiveness endpoint of TIR 70-180 mg/dL, with the range value updated as appropriate.

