6.4 ANALYSIS OF INSULIN REQUIREMENTS

Insulin requirements (TDI, total daily basal insulin and total daily bolus insulin) during the hybrid closed-loop phase will be compared to the standard therapy phase. The insulin requirements will be collected at Visit 2 (start of ST phase) and compared to the data collected by the Horizon[™] System during HCL:

- Total daily insulin: sum of basal and bolus insulin reported over the course of HCL, adjusted for 24-hour period
- Total daily basal insulin: sum of basal insulin reported over the course of HCL, adjusted for 24-hour period
- Total daily bolus insulin: sum of bolus insulin reported over the course of HCL, adjusted for 24-hour period. This will include only bolus insulin administered and recorded by the Horizon[™] System.

Data will be summarized both in insulin units and units/kg to provide a weight-adjusted comparison.

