7.5 HANDLING OF MISSING DATA

All practical monitoring and follow-up steps will be taken to ensure complete and accurate data collection. All analyses will be based on available data only; no imputation for missing data is planned.

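### SAP 7.4 excludes CGM readings taken before standard therapy starts, with no exception for the 14-day record that exempt Dexcom G6 users supply as their Phase 1 data

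*SAP*

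**What the plan says.** **The exclusion.** SAP 7.4 lists two kinds of CGM reading to be left out of the TIR calculations. The first is records with no glucose value. The second includes "CGM readings reported prior to start of standard therapy phase". No exception is attached.

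**When the phase starts.** SAP 6.4 gives the start in passing: "The insulin requirements will be collected at Visit 2 (start of ST phase"). Protocol 8 says "The standard therapy phase will commence after all standard therapy assessments are completed per" Visit 2, and Protocol 8.1 says "Visit 2 represents the commencement of the standard therapy phase". Protocol 12.3.2 equates the start with insertion of the CGM sensor, which Protocol 8.1 lists as a Visit 2 procedure.

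**What exempt G6 users supply.** Protocol 5.2 and 8 let current G6 users provide 14 days of CGM data from the preceding 30 days in place of wearing the study CGM. Under Protocol 7.1 the criteria can be assessed at Visit 1, and the standard therapy phase of those who meet them consists of Visit 2 alone. Protocol 7.1 and Table 1 footnote j allow Visits 1, 2 and 4 on one day, and Visit 4 is the start of HCL.

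**How the values are used.** SAP 4.2 tests the per-subject change in TIR 70-180 mg/dL, Phase 2 minus Phase 1, "using a paired t-test at a one-sided significance level of 1.25" percent. Under SAP 6.1 the secondary TIR endpoints "will follow the analysis set forth for the primary effectiveness endpoint of TIR" 70-180 mg/dL. SAP 7.5 adds that "no imputation for missing data is planned". Where the protocol and SAP disagree, "the content of the SAP shall prevail" (SAP 1; Protocol 13.10 agrees).

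**The concern.** The protocol treats the supplied record as Phase 1 data. The SAP's exclusion rule, taken with the only start date either document gives, removes it. The SAP mentions neither the exemption nor the record. Its only text specific to G6 users, in SAP 5.4, concerns how the safety endpoints are presented.

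A programmer following SAP 7.4 would therefore drop the accepted baseline of an identifiable group. Subjects with no Phase 1 value have no paired difference, and nothing is imputed, so they leave one primary test and both tested secondary endpoints. The loss would not be random, because it is defined by prior G6 use. SAP 4.3 lists previous CGM use as a possible subgroup for the primary endpoints, and literal application would thin that stratum. The alternative is to ignore the rule at the programming stage, which would be an undocumented departure from the SAP on a primary endpoint.

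**Working it through.** **Step 1. Trace an exempt user through the rule.**

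| Situation | Readings before Visit 2 | Readings between Visit 2 and HCL start | Phase 1 value under SAP 7.4 as written |
|---|---|---|---|
| Exempt, Visits 2 and 4 on the same day | the supplied record | none | none, so no pair |
| Exempt, interval between Visits 2 and 4 (for example an MDI user keeping the dose diary for at least 7 days, Protocol 7.1) | the supplied record | possibly some | only from later readings, if any; the accepted record is discarded |
| G6 user who first misses the criteria and keeps collecting until they are met (Protocol 8) | part or all of the record | possibly part | only from the part after Visit 2 |
| Non-G6 user | none needed | at least 14 days of study CGM | unaffected |

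Complete loss of the pair is certain only in the first row.

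**Step 2. Inputs for size.** From SAP 4.1: mean TIR change 10 points, SD of the change 10 points, one-sided alpha 0.0125, power 90%, at least 60 evaluable and up to 80 enrolled. The documents do not give the share of subjects in the first row. I assume 25%, 50% and 75% to show a range.

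**Step 3. The plan's own figure.** SAP 4.1 states that 11 subjects suffice for TIR. With the stated 10/10 inputs and alpha 0.0125:
- Normal approximation: (2.2414 + 1.2816)² × (10/10)² = 12.4, so 13.
- Exact paired t (noncentral t): power is 0.742 at n = 11, 0.898 at n = 15 and 0.921 at n = 16, so 16.

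The figure 11 does come out of the normal approximation at alpha 0.025 (10.5, rounded up). It also comes out of the exact t at alpha 0.0125 if the cited earlier study's 13.2 ± 10.2 is used instead of 10/10. That is a separate matter. Here I use the more demanding 16.

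**Step 4. Precision and power after loss.** Half-width of the 95% CI = t(0.975, n−1) × 10/√n. For example, at n = 60 it is 2.001 × 10/7.746 = 2.58. Power is from the noncentral t with noncentrality √n × 10/10.

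| Assumed share losing their pair | Pairs left of 60 | Half-width (points) | Power | Pairs left of 80 | Half-width (points) | Power |
|---|---|---|---|---|---|---|
| 0% | 60 | 2.6 | >0.999 | 80 | 2.2 | >0.999 |
| 25% | 45 | 3.0 | >0.999 | 60 | 2.6 | >0.999 |
| 50% | 30 | 3.7 | 0.999 | 40 | 3.2 | >0.999 |
| 75% | 15 | 5.5 | 0.898 | 20 | 4.7 | 0.973 |

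**Step 5. Where power would fail.** Power is at least 90% while 16 pairs remain. The study could lose 60 − 16 = 44 pairs (73%) from a base of 60, or 80 − 16 = 64 pairs (80%) from a base of 80.

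**The case against.** The best case on the other side is that nobody would apply the rule this way. SAP 2.3 describes Phase 1 as lasting 14 days, which a same-day starter could satisfy only if the supplied record is that phase. SAP 4.3 says no data are to be left out of the primary analysis of the primary endpoints. The Visit 2 remark in SAP 6.4 is an aside about insulin collection, not a definition of the CGM window. The SAP is silent on where exempt users' Phase 1 data come from, and silence can be filled from the protocol without invoking the precedence clause. A programmer who found a whole subgroup without baseline values would probably ask.

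Most of this stands as evidence of intent: the deletion is unintended. It does not remove the defect. Neither SAP 2.3 nor SAP 4.3 says when standard therapy begins, and every statement in the two documents that does so points to Visit 2. SAP 7.4 is not silent either. It states an exclusion without an exception, and the precedence clause favors it.

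The objection is also right about consequence. SAP 4.2 says the primary effectiveness endpoints will not support labeling claims, and SAP 2.4 rests study success on the severe hypoglycemia and DKA rates alone.

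A reader might go further and infer that all G6 users would drop out, or that the primary test would be underpowered. The documents support neither. Some G6 users may have readings after Visit 2, and power fails only after a loss of about three quarters of 60 pairs.

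**Conclusion.** SAP 7.4 is wrong as written, at low severity. Read with the Visit 2 start date, it removes the part of an exempt G6 user's accepted Phase 1 record that predates Visit 2. It leaves those who start HCL on the same day with no paired TIR value, although they belong to the mITT set under SAP 7.1.2.

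The effect is confined to the TIR comparisons with Phase 1, including the tests of 70-180, >180 and <70 mg/dL. A1C, the safety endpoints and the success criterion are not touched. What is at stake is selective loss of prior G6 users and some precision: with 60 pairs, the half-width would widen from 2.6 to between 3.0 and 5.5 points for assumed losses of 25% to 75%. These figures assume an SD of 10 points and literal application of the rule.

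A reader might also infer a bias in a particular direction. The documents give neither the number affected nor anything from which the size or sign of a selection effect could be derived. Confidence is high about the wording gap; whether any pair would actually be lost depends on how the rule is programmed.

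**What to change.** Add one clause to the second exclusion bullet of SAP 7.4, to this effect: *except that, for G6 users exempt from study CGM wear, the accepted 14-day record supplied under the protocol exemption is their Phase 1 data and is not excluded for being recorded before Visit 2*.

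Keep the first bullet in force, so that records without a glucose value are still dropped from the supplied record. Leave the window for other subjects as it is; this point gives no reason to alter it. In the report, state how many subjects used a supplied record.

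The cost is one clause, one programming definition and one count. The data are already collected under the protocol, and no study procedure changes.

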7.5 HANDLING OF MISSING DATA

All practical monitoring and follow-up steps will be taken to ensure complete and accurate data collection. All analyses will be based on available data only; no imputation for missing data is planned.

7.6 EXPLORATORY ANALYSES

The following exploratory analyses will be considered. The analyses may be used for internal research purposes and/or scientific presentations and/or manuscripts and may not all be provided in a regulatory submission:

- Number of hypoglycemic and hyperglycemic events as measured by the system CGM during the hybrid closed-loop phase will be compared to Phase 1
- Glucose metrics from the system CGM during Phase 2 stratified by device mode
- Change from baseline in A1C and BMI at the last follow-up visit, given at least 8weeks of participation in Phase 2
- Change from baseline in A1C at end of Phase 2, stratified by baseline A1C (e.g. A1C ≥7.5%, ≥9.0%)
- Proportion of subjects with A1C <7.0% at baseline and end of Phase 2; similar analyses using A1C cutoffs of <7.5%, <8.0% and <9.0%
- Proportion of subjects with change from baseline in A1C at end of Phase 2 of >0.5% and >1.0%

- Proportion of subjects who either had an improvement from baseline of >1.0% in A1C or A1C <7.0% at end of Phase 2
- Percentage of time the CGM was used during Phase 2
- Number of meal and correction boluses
- Compare glycemic outcomes (e.g., TIR <70 mg/dL, TIR >180 mg/dL) by bolus frequency per day
- Compare glycemic outcomes (e.g., TIR <70 mg/dL, TIR >180 mg/dL) by use of CGM informed bolus calculator (i.e., days with CGM informed bolus calculator used at least once and days without CGM informed bolus calculator use)
- Glycemic outcomes and other measures based on evaluable subjects (i.e., those subjects with at least 8 weeks of data during Phase 2)

The results of exploratory analyses will be presented using summary statistics. Data at Visit 13 will be used for any parameters that are measured at end of Phase 2 (data at Visit 19 will be used for any parameters that are measured at end of Phase 3). Any statistical testing will be performed at a two-sided significance level of 5% with no adjustment for multiple testing. If the observed data are found not to follow a normal distribution, non-parametric methods may be employed (such as Wilcoxon rank sum test as appropriate).

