2.3 STUDY SCHEDULE

The study will consist of a 14-day outpatient standard therapy (ST) outpatient phase (Phase 1), a 13-week outpatient hybrid closed-loop (HCL) phase (Phase 2), and a 6-month hybrid closed-loop extension phase (Phase 3). The sponsor intends to submit results from Phase 2 for marketing clearance after data collection for Phase 2 is complete.

The Horizon[™] System has two modes. In Manual Mode, the system will function equivalently to the Omnipod DASH System. This includes delivering insulin at programmed basal rates and bolus amounts with the option to set temporary basal profiles. In Automated Mode, the system will support the use of multiple target glucose values. The

Statistical Analysis Plan

programmed basal rates, glucose targets and bolus calculator settings will inform the MPC (model predictive control) algorithm for insulin dosing parameters.

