To gather adequate safety and effectiveness data on the performance of the Omnipod Horizon[™] System, the study plans to enroll up to 80 subjects to obtain a minimum of 60 evaluable subjects. Subjects will be enrolled across 6-12 clinical study sites. No single site should enroll more than 24 subjects.

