6.6 ANALYSIS OF SECONDARY EFFECTIVENESS ENDPOINTS WITHOUT PRESPECIFIED HYPOTHESES

There are no pre-specified hypotheses associated with the other secondary effectiveness endpoints. The mITT analysis set will be the primary analysis set used to analyze the secondary effectiveness endpoints. The results based on the PP analysis set will be considered supportive. Summary statistics will be presented by age cohort for all endpoints, stratified by time points of interest (e.g., day, night, overall). All statistical comparisons will be conducted at a two-sided significance level of 5%, with no adjustment for multiple testing. If the assumptions for parametric tests are grossly violated, a nonparametric method such as Wilcoxon signed rank test may be used. Since the results of endpoint analyses will not be used to support clinical claims, no adjustment for multiplicity will be performed.

As described in this document, results will be stratified by phase of the study (ST and HCL), and time of day (daytime: 6AM to <12AM and nighttime: 12AM to <6AM). Results for other subgroups (e.g., demographics, previous pump or CGM use, length of time in HCL) may be presented as appropriate. Data at Visit 13 will be used for any parameters that are measured at end of Phase 2. Data at Visit 19 will be used for any parameters that are measured at end of Phase 3.

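### SAP 7.6 compares days with and without the CGM-informed bolus calculator but sets no within-child analysis, and the only test it names is for independent samples

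*SAP*

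**What the plan says.** The comparison appears in SAP 7.6 and Protocol 6.4 in the same terms: outcomes such as time below 70 and above 180 mg/dL, set against "days with CGM informed bolus calculator used at least once and days without CGM informed bolus calculator use". The two groups are kinds of day, not kinds of child.

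The status is modest. SAP 7.6 opens with "The following exploratory analyses will be considered" and adds that "The results of exploratory analyses will be presented using summary statistics". Testing is optional: "Any statistical testing will be performed at a two-sided significance level of 5% with no adjustment for multiple testing". If the data are not normal, "non-parametric methods may be employed (such as Wilcoxon rank sum test as appropriate". That sentence covers all twelve analyses in the section. No parametric test is named there.

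Elsewhere the SAP works within the child. Sections 4.2 and 6.5 use per-subject differences with a paired t-test, and section 6.6 says that "a nonparametric method such as Wilcoxon signed rank test may be used". Section 7.6 repeats none of this. The SAP overrides the protocol where they differ, and Protocol 13.8 speaks only of suitable non-parametric methods, so no other text fills the gap.

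**The concern.** Phase 2 lasts 13 weeks, so 60 children give about 60 × 91 = 5,460 child-days. Protocol 2.1.1 leaves it to the user whether the sensor value populates the calculator, so the share of use days can differ between families. If days are pooled, frequent users dominate one group and infrequent users the other. A difference in glycemia between those families then looks like a difference between kinds of day. A rank sum test on the pooled days treats them as independent and does not allow for this. Pooled summary statistics compare the same unequal mixes of children.

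At stake is a possibly misleading statement about one feature of the device. SAP 7.6 allows these analyses to go into presentations and manuscripts.

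**Working it through.** The plan gives no effect size, power or variance for this comparison, so there is no figure to reproduce. The check asks how the named test behaves under each unit of analysis it could be given.

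**Inputs from the documents.** 60 children ("the study plans to enroll up to 80 subjects to obtain a minimum of 60 evaluable subjects"), 91 days each, two-sided 5%.

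**Assumed inputs.** Intraclass correlation ρ of the daily outcome, and the spread of use shares p between children, with mean 0.5. Outcomes are normal, and days are independent within a child. Use share is unrelated to the child's level unless stated.

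**Pooled days, no calculator effect.** Let m be days per child and V the variance of p. Child k enters the difference in pooled means with weight n1k/N1 − n0k/N0. Working out its variance and dividing by the variance that an independent-sample test assumes gives

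R = 1 + 4V(m − 1)ρ, and rejection rate ≈ 2[1 − Φ(1.96/√R)].

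For Beta(a,a) shares, 4V = 1/(2a + 1). With equal shares V = 0, so R = 1 and there is no inflation. With ρ = 0 there is none either.

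Example: ρ = 0.2, Beta(2,2), m = 91. R = 1 + 90 × 0.2/5 = 4.6, √R = 2.145, 1.96/2.145 = 0.914, rejection ≈ 36.1%.

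Simulated rank sum rejection on pooled days (1,000 replicates), with the formula in brackets:

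| ρ | equal shares | Beta(5,5) | Beta(2,2) | Beta(0.5,0.5) |
|---|---|---|---|---|
| 0.05 | 4.9% | 9.8% (9.9%) | 14.9% (15.5%) | 27.3% (27.7%) |
| 0.1 | 5.2% | 13.6% (14.6%) | 21.2% (24.1%) | 38.6% (40.3%) |
| 0.2 | 4.1% | 22.9% (22.7%) | 35.5% (36.1%) | 53.3% (53.5%) |
| 0.3 | 5.2% | 28.7% (29.2%) | 44.3% (43.8%) | 60.1% (60.7%) |

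**The same in points of daily time in range**, with m = 90:
- Mildest case, SD 5 between and 20 within, Beta(20,20): ρ = 25/425 = 0.0588; R = 1 + 89 × 0.0588/41 = 1.128; about 6.5%. Simulation gave 7 to 8%.
- Widest case, SD 10 and 15, Beta(1,1): ρ = 100/325 = 0.308; R = 1 + 89 × 0.308/3 = 10.1; about 54%. Simulation agrees.

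If use share also correlates 0.3 with the child's level (ρ = 0.2, Beta(2,2)), simulated rejection is 87.7%.

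**Child means, pairing ignored.** Each child gives one mean per kind of day, and the two sets are compared by rank sum. For ρ of 0.05 or more, null rejection is 0 to 0.4%. At ρ = 0.2, power is 1.3 to 1.5% for a true effect of 0.1 SD and 78.2 to 84.5% for 0.2 SD.

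**Within-child differences, signed-rank test.** Null rejection is 3.8 to 6.2% over all the scenarios in the table and at ρ = 0. At ρ = 0.2, power for 0.1 SD is 93.5% with Beta(2,2) shares and 96.8% with equal shares; for 0.2 SD it is 100% in the simulation. About 53 of 60 children have both kinds of day under Beta(0.5,0.5), and nearly all under the other distributions.

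**The case against.** A reader might infer that the SAP prescribes a rank sum test on pooled days. It does not. The test is an example, hedged three times, for a whole section in which some analyses compare groups of subjects, where a rank sum test can be suitable. No test is required, and the SAP's per-subject habit elsewhere makes one value per child and kind of day a natural reading. Under that reading the fault is lost power, not false positives. All of this stands. It makes the point a gap in specification rather than a wrong analysis laid down. It does not rescue the example, which fits this comparison under neither unit.

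A reader might also infer that the pooled test responds to differences between children and not to the calculator. That is too strong. At ρ = 0.2 it rejects 77.5 to 94.8% of the time for a true 0.1 SD effect, and at least 99.7% for 0.2 SD. It keeps its level when use shares are equal, however much children differ.

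Finally, the rejection rates rest on variances and use shares that the documents do not give. Daily time below 70 mg/dL is bounded at zero, so a normal model with SD 15 to 20 does not describe it. The rates show direction and possible scale and do not predict this trial.

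**Conclusion.** The point holds as a gap in SAP 7.6: the groups are sets of days shared by the same children, repeated days are not accounted for, and the only test named assumes independent samples.

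If the test is used on pooled days, the 5% level is lost when children differ both in outcome and in share of use days. The loss runs from negligible to about 54% over the assumed SDs with Beta(20,20) to Beta(1,1) shares, and somewhat higher with more extreme shares. If it is used on child means, nearly all power for a 0.1 SD effect goes, though much less for 0.2 SD. A within-child test avoids both faults.

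The documents do not support a claim that inflated error is certain, or that it touches the trial's conclusions. The analysis is optional and exploratory, may not be submitted, and bears on no primary, secondary or success criterion. This is a minor improvement, worth making before the analysis is run.

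**What to change.** Add to SAP 7.6, for this comparison: for each child, take the mean outcome on days with use minus the mean on days without use. Summarise these differences and, if a test is done, use a paired t-test or Wilcoxon signed-rank test. A mixed model of daily values with a child random intercept and use centred within child is an alternative, though it fits a bounded, skewed outcome such as time below 70 mg/dL less well. Describe children with only one kind of day, without testing them.

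The cost is SAP wording and slightly different programming, with no new data. Children who always or never use the calculator drop out of the test, so the result speaks only for those with both kinds of day. Confounding between days remains: days on which a family uses the calculator may differ in other ways, so the result should still be reported as an association.
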